7.9 Concomitant Medications

7.9.1 Prohibited Concomitant Medications

Current use of anti-coagulants (e.g., warfarin (Coumadin), dabigatran (Pradaxa) or anti-platelet drugs (e.g., Plavix) see section 12.1.1, other than aspirin up to a dose of 325 mg per day, is prohibited. Prospective subjects who in consultation with the prescribing physician can safely discontinue these medications for 4 weeks before screening and remain off these medications throughout the study, can be considered for inclusion in the study.

Use of the following medications is prohibited within 4 weeks of screening and throughout the study:

- tricyclic antidepressants
- antipsychotics prescribed for any reason, except ≤ 50 mg quetiapine daily, risperidone ≤ 1.5 mg/day, olanzapine ≤ 5 mg/day, and aripiprazole ≤ 10 mg/day
- psychostimulants

Investigational agents are prohibited 4 weeks prior to entry and for the duration of the trial.

Initiation of prohibited medications during the course of the study is discouraged, however, if an excluded medication is initiated after screening, the site should consult with the Project Directors and Medical Monitor for further guidance.

7.9.2 Permitted Concomitant Medications

This protocol allows concomitant treatment with anti-parkinsonian medications at stable doses for 4 weeks or greater prior to screening and with cholinesterase inhibitors and/or memantine if on a stable dose (FDA approved drug ranges) for at least 12 weeks prior to screening.

Anticonvulsant medications used for epilepsy or mood stabilization; neuropathic pain indications. Dosing must be stable for at least 4 weeks prior to Screening.

Mood-stabilizing psychotropic agents, including but not limited to lithium. Dosing must be stable for at least 4 weeks prior to Screening.

Use of short acting benzodiazepines and hypnotics for treatment on an as-needed basis for insomnia or daily dosing as anxiolytics is permitted but should be avoided for 8 hours before administration of cognitive tests. If sedating medication is given for any short-term use, then all cognitive assessments must be administered at least 24 hours after administration of the sedative.

8 STUDY POPULATION

Participants in this study must be in accordance with the criteria specified below. Subjects who do not meet all inclusion criteria, disease diagnostic criteria, or who meet any exclusion criteria may not be randomized into the study without prior approval from the Project Directors and Medical Monitor.

8.1 Inclusion Criteria

Subjects must meet the following criteria:

1. Male or female aged 45 years and over.
2. Female participants must be of non-childbearing potential or post-menopausal for at least 2 consecutive years or surgically sterile (bilateral tubal ligation, hysterectomy or bilateral oophorectomy) for at least 6 months prior to screening.
3. Female participants will be given a urine pregnancy test at the screening visit for which they should test negative.
4. A) AD - CDR = 0.5 or 1.
B) PD - Hoehn & Yahr ≤ 4 ; PD criteria by MDS-UPDRS.
5. A) AD MMSE score between the range of 18 to 28.
B) PD MMSE score between the range of 18 to 30.
6. General cognition and functional performance sufficiently preserved that the subject can provide written informed consent.
7. No evidence of current suicidal ideation or previous suicide attempt in the past month as evaluated in the Columbia Suicide Severity Rating Scale.
8. MRI scan within the 12 months prior to screening without evidence of infection, infarction, or other focal lesions and without clinical symptoms suggestive of intervening neurological disease. Lacunes that are not believed to contribute to the subject's cognitive impairment are permissible. If there is no MRI available within a 12-month timeframe, then an MRI must be performed as part of the screening procedures for eligibility.
9. Stability of permitted medications prior to screening.
 - a. Stable for at least 12 weeks: Cholinesterase inhibitors and/or memantine medication
 - b. Stable for at least 4 weeks:
 - i. Anti-parkinsonian medication
 - ii. Anticonvulsant medications used for epilepsy or mood stabilization; neuropathic pain indications
 - iii. Mood-stabilizing psychotropic agents, including, but not limited to, lithium.

10. Adequate visual and hearing ability (physical ability to perform all the study assessments).
11. Good general health with no disease expected to interfere with the study.
12. Subjects previously exposed to Posiphen may be included in the study.

8.2 **Exclusion Criteria**

Subjects meeting any of the following criteria must not be included in the study:

1. Has a history of a psychiatric disorder such as schizophrenia, bipolar disorder or major depression according to the criteria of the most current version of the Diagnostic and Statistical Manual of Mental Disorders (DSM). Mild depression or history of depression that is stable on treatment with a SSRI or SNRI medication at a stable dose is acceptable.
2. History of a seizure disorder.
3. Has a history or current evidence of long QT syndrome, Fridericia's formula corrected QT (QTcF) interval \geq 450ms, or torsades de pointes.
4. Has bradycardia (<50 bpm) or tachycardia (>100 bpm) on the ECG at screening.
5. Has uncontrolled Type-1 or Type-2 diabetes . A Subject with HbA1c levels up to 7.5% can be enrolled if the investigator believes the subject's diabetes is under control.
6. Has clinically significant renal or hepatic impairment.
7. Has any clinically significant abnormal laboratory values. Subjects with liver function tests (aspartate aminotransferase [AST] or alanine aminotransferase [ALT]) greater than twice the upper limit of normal will be excluded.
8. Is at imminent risk of self-harm, based on clinical interview and responses on the C SSRS, or of harm to others in the opinion of the Investigators. Subjects must be excluded if they report suicidal ideation with intent, with or without a plan or method (e.g. positive response to Items 4 or 5 in assessment of suicidal ideation on the C SSRS) in the past 2 months, or suicidal behavior in the past 6 months.
9. Has four or more signal hypointensities on T2*-weighted gradient recalled echo magnetic resonance sequences that are thought to represent hemosiderin deposits including microhemorrhages and superficial siderosis or evidence of acute or sub-acute micro or microhemorrhage as noted on the MRI scan.
10. Has cancer or has had a malignant tumor within the past year, except patients who underwent potentially curative therapy with no evidence of recurrence. (Patients with stable untreated prostate cancer or skin cancers are not excluded).

11. Alcohol / Substance use disorder, moderate to severe, in the last 5 years according to the most current version DSM.
12. Participation in another clinical trial with an investigational agent and have taken at least one dose of study medication, unless unblinded on placebo, within 60 days prior to the start of screening. (The end of a previous investigational trial is the date the last dose of an investigational agent was taken), or five half-lives of the investigational drug, whichever is greater.
13. Subjects with infection or inflammation of the skin or skin disease at or in proximity to the lumbar puncture site.
14. History of lumbar spine surgery or chronic low back pain (CLBP).
15. Subjects with learning disability or developmental delay.
16. Subjects whom the site PI deems to be otherwise ineligible.

9 DESCRIPTION OF STUDY VISITS

Each subject will have a 42-day screening period followed by 25±2 days of treatment at home. The study visits are described below and outlined in the Schedule of Events in [Appendix 1](#).

9.1 Screening Visit

The screening visit should occur up to 42 days before the baseline visit. The screening visit procedures may be completed over multiple days.

Potential participants, or legally authorized representatives, and their study partners must sign an informed consent form prior to administration of any study-related procedures. Information regarding the subject's demographics, concurrent medications, and medical history will be collected along with cognitive assessments, physical examination, and neurological examination.

Safety assessments will include an MRI scan (up to 12 months prior) and ECG that will need to be read locally and reviewed by the site investigator to confirm eligibility. The clinical safety laboratory blood and urine tests will be sent to a central lab for analysis. The screening safety laboratory tests will be comprised of a metabolic panel, complete blood count, coagulation panel, and urinalysis as listed in Section 12.1.3. Coagulation panel results must be obtained prior to performing the lumbar puncture. Urine dipstick pregnancy test will be completed for female subjects.

Cognitive and functional assessments should not be administered when the subject is in a fasted state. Once all screening visit procedures are completed, all information related to eligibility, including screening lab results, must be reviewed by the site investigator to assess the subject's eligibility before proceeding to Baseline.

Sites should try to enroll patients who already have an MRI scan available to limit patient burden. Any patient who requires a new MRI **must** have all other screening assessments completed prior to performing the MRI.

9.2 Baseline Visit

Baseline procedures include functional, cognitive, and behavioral assessments, safety assessments, and review of concurrent medications and adverse events that occur in clinic.

Following completion of all baseline procedures, subjects who continue to meet all protocol inclusion criteria and no exclusion criteria, should be scheduled for the confinement visit. The subject should then be randomized, dispensed study drug, and instructed on proper storage and at-home dosing based on the scheduled date of the confinement visit. The subject should be instructed on 1.) to take the first dose immediately after the baseline spinal tap and venipuncture 2.) the Day 14 Contact and the Pre-Confinement Phone Contact and 3.) Study drug compliance and study drug return.

A lumbar puncture will be performed as part of the baseline visit, in the morning (before 10 am is recommended), after an overnight fast. After the collection of the baseline lumbar puncture and venipuncture, the first dose of Posiphen will be administered to the patient.

The subject will stay at the unit for a 1 hour observation period and may be safely discharged to home per investigator discretion. Subjects will have the option to stay overnight in the occurrence of adverse events associated with the LP procedure.

Subject baseline visit can be split over two (2) consecutive days should the investigator feel that the neuropsychological tests are better completed without fatigue (i.e., after LP or unfasted).

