9.4.2 Confinement Visit

The confinement visit will consist of the following: admission procedures, Time 0 blood and CSF sampling, administration of last dose of study drug, 6-hours of blood and CSF sampling, at least a 1-hour observation period while subject remains on bed rest with the observation period

to be extended as clinically necessary as per the Investigator's decision, and discharge procedures. Subjects will be provided with sleeping accommodations during this visit, if necessary, and maybe permitted to remain overnight per investigator discretion in the event there are adverse events associated with the study medications or study procedures.

Subject confinement visit can be split over two (2) consecutive days should the investigator feel that the neuropsychological tests are better completed one day before the lumbar puncture.

Period 1: Admission

Subjects should arrive fasted in the early morning after an overnight fast. Clinical safety labs will be drawn and sent to the central lab for analysis.

Study drug compliance over the preceding days will be assessed. If there is an insufficient level of drug compliance (less than 80% overall), the site must consult with the Project Directors and Medical Monitor) regarding timing and conduct of the remaining confinement visit procedures. It is possible that subjects will be discontinued early from the study due to insufficient study drug compliance.

Admission visit procedures include conducting a Physical and Neurological Exam, administering functional and cognitive evaluations and C-SSRS, collecting vital signs, ECG, clinical labs, reviewing and recording adverse events and concurrent medications.

Period 2: 6-Hour Sampling

If no medical or compliance concerns are identified during the admission procedures, the subject will move on to the 6-Hour Sampling Phase, which entails the following procedures:

1. Place an intravenous line for blood sampling. Alternatively, blood may be sampled by direct venipuncture if deemed appropriate by the PI.
2. Place the CSF catheter.
3. Collect initial samples of blood and CSF (Hour 0).
4. Administer last dose of assigned study drug after the 0 hour sampling.
 - a. Collect CSF (6 mL) and blood (10mL) every hour at the following time points: 1, 2, 3, 4, 5, 6 hours.
 - i. CSF and blood should be taken within \pm 10 mins of hourly times.

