5.6 Other Definitions

Baseline, Study Day and Event Duration are specifically defined as:

Baseline

Two baselines are defined:

- 1 Last assessment prior to first dose of study IMP on Day 0.
- 2 At 0 hours on Day 25 of the Confinement visit

Study Day

Study Day = (Date of event - first dose of study IMP) + 1.

Event Duration

Event Duration= (Date of resolution – Date of onset) + 1

6. Statistical Methods.

This statistical analysis plan specifies the requirements for the analysis and reporting of all data collected during the study.

All analyses and data reporting procedures will be undertaken using SAS® v9.4 in a Windows version 10 operating system environment.

The descriptive statistics produced will account for the nature and distribution of the data collected. For continuous variables (actual and percentage change from baseline), data will be presented as number (n), mean, median, standard deviation, and range. For discrete variables (Incidence, Response outcome) data will be presented as frequencies and proportions and the denominator will be the number of patients available.

Data collected from patients in each of the three cohorts (Part 1 AD, Part 1 PD, Part 2 PD) will be derived and summarised as described in section 5 and analysed according to the defined analysis population in section 4.

All comparisons of primary interest performed in Part 1 and Part 2 involve changes from baseline (Within treatment group). The null hypothesis throughout is that there is no difference between the Day 25 end of treatment and Pre-treatment baseline (H0. $X_{end}=X_{base}$, H1. $X_{end} \neq X_{base}$).

Between treatment groups comparisons are also possible (but of secondary interest due to the small sample size). Here the null hypothesis is that there is no difference between any of the treatment groups at the end of treatment (H0. Placebo= $X_{5mg}=X_{10mg}=X_{20mg}=X_{40mg}=X_{80mg}$, H1. Placebo $\neq X_{5mg} \neq X_{10mg} \neq X_{20mg} \neq X_{40mg} \neq X_{80mg}$).

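### The split-visit wording in Protocol 9.2 lets baseline cognitive and functional tests fall after the first dose, against 9.2's own order and the SAP 5.6 baseline

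*Protocol*

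**What the plan says.** **Baseline visit (Protocol 9.2).** Functional and cognitive assessments are listed among the baseline procedures. Once all baseline procedures are complete, an eligible subject is scheduled for confinement, randomized and given drug. On the LP: "A lumbar puncture will be performed as part of the baseline visit, in the morning (before 10 am is recommended), after an overnight fast". On the dose: "After the collection of the baseline lumbar puncture and venipuncture, the first dose of Posiphen will be administered to the patient", and the subject is told "to take the first dose immediately after the baseline spinal tap and venipuncture". The visit may be spread over two consecutive days if the investigator feels that "the neuropsychological tests are better completed without fatigue (i.e., after LP or unfasted". Nothing says which of the two days is the test day.

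**Fasting (Protocol 9.1, Screening Visit).** "Cognitive and functional assessments should not be administered when the subject is in a fasted state". The sentence is general in wording but is not repeated for baseline or confinement.

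**Confinement (Protocol 9.4.2).** "Subjects should arrive fasted in the early morning after an overnight fast". The tests are an admission procedure, before the 0-hour sample and the last dose. This visit may also be split, but here the order is stated: "neuropsychological tests are better completed one day before the lumbar puncture".

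**Analysis (SAP).** Section 5.6 defines the pre-treatment baseline as "Last assessment prior to first dose of study IMP on Day 0". Section 6.2 analyses Day 25 minus Day 0. Sections 2 and 6 make within-group change from baseline the comparison of main interest, and 5.5 rules out imputation.

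**The concern.** The first dose is tied to the LP, so a test done after the LP is, on the protocol's timing, a test done after the first dose. The bracket in 9.2 appears to offer that as an acceptable arrangement, and a site could follow it in good faith.

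The main comparison for these scores is within group, so a difference in test conditions between the two visits goes straight into the estimated change. Protocol 3.2 reports peak concentration at about 1.2 to 1.5 hours, so a same-day test soon after the LP and dose could fall near peak, while Day 25 admission tests precede that day's dose. Protocol 2 wants these measures to help show that the drug does no harm to function and cognition. SAP 2.1.2 wants them as variability estimates for later trials. SAP 7.2.3 makes formal analysis depend on whether a notable change from baseline is seen. Each of these uses needs a baseline with a clear meaning.

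**Working it through.** No sample-size or power figure bears on this point. The check is one of order, using the rules set out above.

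**1. Split baseline visit.** There are two possible orders, and 9.2 excludes neither in its split sentence.
- Tests the day before the LP: before the first dose, and can be unfasted.
- Tests the day after the LP: after the first dose.

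The second order breaks the sequence in 9.2 (procedures, then randomization and dispensing) and does not meet SAP 5.6. It is nonetheless the order that the words about testing after the LP describe.

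**2. One-day baseline visit.** Take four events: first meal, tests, LP, first dose. They can be ordered in 4! = 24 ways. The LP must precede the meal (overnight fast) and the dose. Adding the other rules gives:

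| Rules applied | Orders that comply |
|---|---|
| Tests unfasted, tests pre-dose, dose immediately after LP | 0 of 24 |
| As above, but tests may be post-dose | 1: LP, dose, meal, tests |
| As above, but fasting sentence limited to screening (tests pre-dose) | 1: tests, LP, dose, meal |
| As above, but dose not immediate (tests unfasted and pre-dose) | 1: LP, meal, tests, dose |

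So the one-day visit is blocked only if the 9.1 sentence reaches beyond screening. If it does not, testing before the LP complies. The last row only shows which rule binds; the timing of the dose is not at issue here.

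**3. One-day confinement visit.** The subject arrives fasted and is tested at admission, before the 0-hour sample. Protocol 12.2.4 relaxes fasting only after that sample, and says so for the exosome draws. One-day Day 25 tests are therefore fasted and before that day's dose. That matches a one-day baseline with tests before the LP. It does not match a baseline taken after the LP and dose.

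**4. Effect of a post-dose baseline test under SAP 5.6.** From the Schedule of Events:

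| Instrument | Screening | Baseline | Admission | Pre-dose value if the baseline test is post-dose |
|---|---|---|---|---|
| MMSE (AD, PD) | yes | yes | yes | Screening, up to 42 days before baseline |
| CDR (AD) | yes | yes | yes | Screening, up to 42 days before baseline |
| WAIS-IV (AD, PD) | no | yes | yes | None |
| ADAS-Cog 14 (AD) | no | yes | yes | None |
| MDS-UPDRS (PD) | Hoehn & Yahr stage only | yes | yes | None for part or total scores |

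Per patient, 2 of 4 instruments in AD and 2 of 3 in PD have no fallback.

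**5. Scale.** In a planned active group of 10, one such patient is 1/10 = 10% of the change data on those instruments. In a placebo group of 4, it is 1/4 = 25%. These figures describe one hypothetical patient and say nothing about how often this occurs.

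**The case against.** The other side has good arguments, and several of them stand.

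- **Section 9.2 already puts tests before dosing.** Read as a whole, it completes baseline procedures before randomization and dispensing, so post-dose testing would breach it. This stands, and it makes a fasted test before the LP the likelier one-day outcome. It does not remove the split sentence, which points the other way.
- **The bracket is garbled.** It may have been meant to describe what causes fatigue, with the last word a slip. The clear order given for confinement supports that intent. But a site has only the wording in front of it, and the wording names testing after the LP.
- **The fasting sentence may be for screening only.** It sits among screening procedures. Its general phrasing and the mention of unfasted testing in 9.2 suggest wider reach, but the text does not settle it. A reader might infer that a one-day baseline visit has no compliant pre-dose slot at all. The documents support that only on the wider reading.
- **Conditions may match.** A reader might also infer that post-dose baselines will be set against fasted Day 25 scores across the trial. That needs the two visits to be handled differently. If both are one-day with tests first, both are fasted and pre-dose. If both are split with tests first, both can be unfasted.
- **The endpoints are exploratory.** Protocol 4.2 calls clinical benefit unlikely, and SAP 2.1.2 does not expect it. Part 1 also has a randomized, though small, placebo comparison under the same procedures. Both points limit the consequences.

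**Conclusion.** The point holds as a conflict between passages that must be reconciled: the split sentence in 9.2 permits baseline tests after the first dose, while 9.2's own sequence and SAP 5.6 require them before it. This does not depend on how the fasting sentence is read. Whether that sentence covers baseline and confinement is a second, open question.

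For an affected patient the two harms are alternatives. If the visit-based wording of SAP 5.2.2 and 6.2 governs, a post-dose score becomes the baseline and the change mixes test conditions with drug effect. If SAP 5.6 is applied strictly, two instruments have no baseline and the patient leaves those change analyses, while MMSE (and CDR in AD) reverts to screening.

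The documents do not show that bias will occur, or that all 68 planned patients are affected, because a tests-first visit avoids a post-dose baseline. The frequency depends on site practice and is unknown. The point is worth correcting because the within-group comparison has no other protection, and without recorded times the problem might not be detectable afterwards.

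**What to change.** 1. **Protocol 9.2.** Replace the bracketed phrase with a statement that all cognitive and functional tests are completed before the baseline LP and the first dose and, if the visit is split, on its first day.
2. **Protocol 9.1, 9.2 and 9.4.2.** State whether the sentence against fasted testing applies to baseline and confinement. Test each patient in the same fed or fasted state and the same visit format (one-day or split) at both visits.
3. **eCRF.** Record fed or fasted status at testing, and the clock times of the tests, the LP and the first dose.
4. **SAP 5.6 and 6.2.** Flag any baseline test taken after the first dose, and show the results with and without those values.

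The cost is a wording change, a few eCRF fields, one extra set of outputs and less scheduling freedom for sites. No dosing rule changes. The fix does not itself impose two-day visits: tests before the LP on a single day remain possible if the fasting sentence is confined to screening. If the sponsor extends that sentence to all visits, the existing LP and dosing rules leave only the split format, and that burden should be weighed when the decision is made.
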